3.6.4 Glycaemic control and other biochemical disease parameters

We will compare recorded plasma glucose concentration, HbA1c values, and other objective disease parameters before and after the baseline. Because the date of dispensation/issue does not precisely indicate the exact date of patient medication switch, we do not know the precise day that the patient starts the new medication), it will be important to explore different time windows after the recorded dispensation/issue date. We will compare measurements at various time points before and after the baseline. The latest measurement before the baseline will be assumed to indicate the baseline value for the analysis. The follow-up time after baseline is expected to vary depending on the date of available laboratory testing. We will conduct analyses examining 1, 3, and 6-month post-baseline changes in laboratory parameters.

Furthermore, we will examine the potential role of secular trends – scientific or media publications and EMA warnings – by controlling in the analysis for time elapsed from an event that could potentially trigger medication switch and the time of actual switch (approximated by the date of the new prescription). We propose that recency of potential triggering events may be an indirect indicator of patient's underlying risk of potential adverse events as perceived by patients themselves or their providers.

4 Quality assurance, feasibility and reporting

This study will be carried out by scientists employed at academic institutions. The study in Denmark will be conducted by the study coordinator, the Department of Clinical Epidemiology (DCE), Aarhus University, Denmark. The study in the UK will be conducted by the Boston Collaborative Drug Surveillance Program (BCDSP), which is an independent research unit affiliated with Boston University, USA. The study was commissioned to the Department of Clinical Epidemiology by the European Medicines Agency. EMA is the sole sponsor of the study. Because

EMA required that data from at least two EU Member States be included in this evaluation, DCE subcontracted BCDSP to conduct the analyses in the United Kingdom.

The Department of Clinical Epidemiology has 10-year experience in registry-based research in Denmark. Most of the databases that will be used for linkage in this study are in-house at DCE. As of 2010, the BCDSP has had 21 years of experience with the organization, validation, and research use of the GPRD. The DCE has access to all data necessary to conduct this study in Denmark, while BCDSP has access to all data necessary to conduct this study in the GPRD. The researchers in both institutions have extensive experience working with and publishing from these data sources.

The core research team will consist of epidemiologists and biostatisticians with experience in drug safety studies; for clinical and laboratory data extraction, and results' interpretation, an experienced diabetologist will be consulted. Data linkage, extraction, coding, and management will be conducted by experienced statisticians, using established institutional facilities, including secure servers. Data analysis will be performed using SAS statistical software (SAS, Inc., Cary, NC, USA). The interim report will include data available in time to prepare the report by the deadline for the interim report (1 April 2011). The final report will be the update of the interim report with the data that become available in time for inclusion to the final report (1 October 2011). The milestones for data collection, analysis, and final report submission have been established and agreed upon with the funding agency. Appendix 2 (Research Contract) includes the milestones.

Validation studies of Denmark's registries and of GPRD have shown satisfactory data validity in these sources for research purposes.^{20,21} All data sources are updated regularly.

Sources of systematic error in epidemiologic studies include selection bias, information bias and confounding. Because of routine data collection in the data sources involved, selection bias is expected to be negligible. Information bias may stem from inability to ascertain the actual drug intake from prescription issue or dispensation data; however, because of chronic nature of the underlying condition, high compliance with oral glucose-lowering drug may be assumed, although timing of medication switch remains as a source of uncertainty and is a limitation. Another limitation is potential residual confounding by lifestyle factors, such as alcohol, diet and smoking, which are only partially or not at all recorded in the available data sources.

The study is feasible: based on preliminary data linkage, currently there are about 2,400 users of rosiglitazone preparations recorded in the Aarhus University Prescription Database and approximately 20,000 users of rosiglitazone preparations can be identified in the GPRD. Majority of these users also have available laboratory data. Because the study will be based on linkage of routine records, no appreciable patient attrition is expected, and follow-up end can be ascertained exactly by obtaining data on dates of emigration and death.

5 Ethical issues

The Danish Data Protection Law requires that approval be obtained from the Data Protection Agency for use of registry data. The Department of Clinical Epidemiology has obtained all approvals necessary to conduct his project.

All studies conducted using the GPRD must be approved by the Independent Scientific Advisory Committee. The BCDSP is in the process of obtaining this approval.

6 Data sources and linkage

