3.4.4 Glycaemic control

Glycaemic control will be assessed by examining levels of blood glucose concentration and glycated (glycosylated) haemoglobin A (HbA1c), or both, whenever available. Plasma glucose concentration fluctuates in response to food intake, and fasting state of patients is not always ascertainable. Haemoglobin A in the red blood cells binds to plasma glucose, becoming irreversibly glycated for the duration of the erythrocytes' lifespan. Thus, HbA1c represents a summary of glucose values over the preceding 1 – 4 months both in fasting and postprandial states. The proportion of glycated haemoglobin A is linearly related to long-term blood glucose concentration and is currently a standard measure of long-term glycaemic control.¹⁸

Results of laboratory investigations will be ascertained from the Laboratory Information Systems of the North and the Central Denmark Regions (LABKA database) in Denmark and from the GPRD's Laboratory File, in the UK. Relevant codes are provided in Appendix 1.

We will use the following measures of plasma glucose concentration (differentiating fasting from non-fasting patients whenever available):

- Mean and median change;
- Percent change from the baseline value;

- Treatment failure, defined as fasting plasma glucose level >180 mg per decilitre.

We will use the following measures of HbA1c:

- Mean and median change;
- Percent change from the baseline value;
- Results of 120-minute glucose tolerance test (standard measure of diabetes; possibly in Denmark)
- Loss of glycaemic control, defined as of HbA1c level >7.5%.

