3.6.3 Acute drug reactions

For patient-level endpoints, baseline will be defined as the recorded date of medication switch/addition (as reflected by a new dispensation/issue); date of the first-time prescription dispensation/issue (in first-time users) or 1 January 2000 (in prevalent users).

We will examine the number of potential drug reactions occurring within 45 days of baseline and calculate the 45-day cumulative incidence of acute drug reactions, overall and diagnosis-specific (if the data set is large enough); We will estimate risk ratios for the acute drug reactions identified using regression, while adjusting for confounding.

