6.1 Denmark

The Aarhus University Prescription Database records all reimbursed prescriptions dispensed in community pharmacies of the North and Central Denmark Regions – 2 of the 5 Danish regions, with combined population of 1.8 million, or 30% of the entire Denmark's population. Prescriptions for oral glucose-lowering medications are eligible for general reimbursement and are therefore recorded in this database; more than 98% of antidiabetic prescriptions are dispensed in the primary sector,² and are therefore expected to be recorded in this database. Recorded information includes the Anatomical Therapeutic Chemical classification of the drug, date of the dispensation, and unique product number.

Laboratory Information Systems for North and Central Denmark Regions (LABKA) track all hospital-performed laboratory tests, including those sent to hospital laboratories by general practice. The following data are recorded: the test name and IUPAC-code, the result, the measurement unit, the dates of ordering and carrying each test. The current coverage period for the Central Region ~ October 1999 to September of 2009, inclusive, for the North Region from 1997 to 2008, inclusive.

The Danish Central Personal Registry covers the entire Danish population and since 1968 has registered all births, deaths, and migration of Danish residents. This database contains dates of all recorded events and is updated daily.

The Danish Registry of Causes of Death contains information on causes of death, including associated diagnoses. Data have been collected since 1970.

The Danish National Registry of Patients covers the entire Danish population and has registered hospitalizations since 1977, including outpatient visits since 1995. Up to 20 discharge diagnoses are recorded for each hospital contact, using the International Classification of Diseases 10th revision (ICD-10) since 1994 and ICD-8 in the earlier period.

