The Danish National Indicator Project (DNIP) was established in 1999 as a national quality monitoring and development project, aiming to measure and improve core healthcare services by means of indicators (indicator monitoring). During 2000–2008, disease-specific, evidence-based indicator sets for selected conditions –including diabetes – have been developed and implemented. The DNIP registration form for diabetic patients includes variables for date of diagnosis, date of diagnosis and type of diabetes, smoking habits, body mass index, blood pressure measurement, and HbA1c. This database is updated quarterly with a delay of one quarter. The latest update was in June 2010. Supplementary data on some rosiglitazone users may be available from the Danish National Indicator Project for Diabetes (DNIP)²², which was established in 1999 and collects annual measurements on HbA1c, smoking, body mass index, and blood pressure of diabetic patients in Denmark. For this project, we will apply for access and link the study population data with the DNIP files, although the extent of data overlap cannot be determined until the data are linked. Another shortcoming of these data is that only the most recent measurement in each calendar year is recorded, which does not necessarily represent the measurement most relevant to medication switch. At the same time, DNIP files may provide information on smoking and obesity for some of the diabetic patients.

Data linkage. All data sources listed above can be linked on patient level by the unique civil registration number, which is used to identify persons in all Danish registries. This number encodes person's sex and date of birth, enabling calculation of age at each time point or event.²³

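### The laboratory baseline is the latest earlier value, with no maximum age and no requirement that it was taken on the regimen being left

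*Protocol*

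**What the plan says.** Section 3.6.3 of the protocol fixes the baseline date. For switchers and adders, "baseline will be defined as the recorded date of medication switch/addition (as reflected by a new dispensation/issue"). First-time users take the date of their first prescription, and prevalent users take 1 January 2000.

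Section 3.6.4 fixes the value attached to that date: "The latest measurement before the baseline will be assumed to indicate the baseline value for the analysis". The outcome is then read at set times: "We will conduct analyses examining 1, 3, and 6-month post-baseline changes in laboratory parameters".

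Two other sentences in 3.6.4 concern timing. One looks forward only: "it will be important to explore different time windows after the recorded dispensation/issue date". The other is general: "We will compare measurements at various time points before and after the baseline". Neither sets a look-back limit.

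Section 3.4.4 describes what one HbA1c value measures: "HbA1c represents a summary of glucose values over the preceding 1 – 4 months". Section 6.1 gives the coverage of the Danish laboratory database (LABKA): from about October 1999 to September 2009 for the Central Region, and "for the North Region from 1997 to 2008, inclusive". For the supplementary Danish indicator data (DNIP), section 6.1 notes that "only the most recent measurement in each calendar year is recorded", and concedes that this value may not be the one that matters for the switch.

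**The concern.** Tests are done in routine care, with no scheduled visits. The latest value on file may be recent or old, and the rule treats both alike. Two separate problems follow.

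- **Age.** A change labelled as 1-month can span the whole interval since the last test, so any drift over that interval is counted as part of the change at the switch.
- **Regimen.** Section 3.3 expects successive therapies: patients leaving rosiglitazone may have taken other oral drugs before it. If the latest value predates rosiglitazone, the computed change spans two treatment changes. An HbA1c taken soon after rosiglitazone was started would still partly reflect the drug before it.

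A smaller matter is that, read literally, a test on the baseline date itself is not before baseline and is left out, although an HbA1c from that day still describes the preceding months.

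At stake is the fifth specific aim, disease control in patients who switch to or from rosiglitazone. Mean change, median change and percent change in 3.4.4, and the changes in 3.4.5, all start from this value.

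**Working it through.** The protocol gives no figure on this point, so there is nothing to reproduce. The check is what the written rule allows.

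**Inputs.** LABKA start: 1 October 1999 for Central (the protocol says approximately October 1999; the first of the month is my reading) and 1 January 1997 for North. LABKA end: 30 September 2009 and 31 December 2008 (section 6.1). Baseline dates: the starts of Periods 2 and 3 in section 3.6.1, and 1 January 2000 for prevalent users (section 3.6.3).

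**Formula.** Maximum permitted age = baseline date − first date of laboratory coverage.

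| Baseline date | Central | North |
|---|---|---|
| 24 May 2007 | 91.7 months = 7.6 years | 124.7 months = 10.4 years |
| 25 January 2008 | 99.8 months = 8.3 years | 132.8 months = 11.1 years |
| Latest switch with 6 months of follow-up inside coverage | 10.0 − 0.5 = 9.5 years | 12.0 − 0.5 = 11.5 years |
| 1 January 2000 (prevalent users) | 3.0 months | 36.0 months = 3.0 years |

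The suspension date of 23 September 2010 is not used. The coverage stated as current ends before it in both regions, so LABKA would supply no post-switch value there unless it is extended. For the UK, the protocol gives no start date for laboratory data, so no maximum is computed, but the same unbounded rule applies.

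**Against the measurement.** Section 3.4.4 gives one HbA1c value a reach of 1 to 4 months. Every maximum in the table exceeds 4 months except that for Central Region prevalent users.

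**Illustration of size, on assumptions not in the documents.** Suppose HbA1c rises 0.1 to 0.3 percentage points per year before a switch and the baseline is 2 years old.

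- Shift = 2 × 0.1 to 2 × 0.3 = 0.2 to 0.6 points.
- A true change of −0.5 would appear as −0.5 + 0.2 = −0.3, up to −0.5 + 0.6 = +0.1.

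The direction is assumed too. A high value taken before the regimen being left was started would bias the change the other way.

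**The case against.** The strongest reply is that the latest earlier value is already the freshest on record, and that a look-back limit is the kind of detail a separate analysis plan adds. A missing window alone would indeed be no finding. Here, however, section 3.6 is itself the analysis plan to which section 3.4.5 refers the reader for the definition of baseline. The rule is written there without a bound, so following it literally admits any earlier value. The sentence on comparing various time points before and after baseline shows that other pre-baseline comparisons are planned, but it leaves the rule unchanged.

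Several stronger readings are tempting, and the documents do not support them:

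- **That baselines will typically be years old.** The ages above are what the rule permits. A years-old baseline for a 1-month change needs a patient untested for years and then tested about a month after switching. How often that happens cannot be told from the protocol.
- **That any HbA1c older than 4 months is uninformative about the drug being left.** A patient on one drug for three years with an 8-month-old value still has a value that reflects that drug. Age and regimen are separate conditions.
- **That the Denmark–UK comparison is distorted.** The only quantitative cross-country comparison, in section 3.6.1, concerns prescribing. None is planned for laboratory change.
- **That Danish HbA1c baselines depend on DNIP.** Section 3.4.4 names LABKA and the GPRD Laboratory File as sources. Section 3.4.5 uses the indicator data only for blood pressure in a subset, and section 6.1 calls DNIP supplementary and discloses its timing weakness.

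**Conclusion.** The point holds as a defect in a stated rule. The protocol fixes the laboratory baseline with no maximum age and no on-regimen condition, and so permits a reference value that its own account of HbA1c would not treat as describing control at the switch. The permitted age reaches about 7.6 years (Central) and 10.4 years (North) for a switch on 24 May 2007, taking the section 6.1 coverage dates at face value.

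The size of any resulting bias is not established. The share of patients with an old or wrong-regimen baseline is unknown, regularly tested patients would be little affected, and the 0.2 to 0.6 point shift rests wholly on an assumed drift and an assumed 2-year age. The change is worth making because it is cheap and uses dates the study already plans to hold, not because large bias has been shown.

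**What to change.** Replace the baseline sentence in section 3.6.4 with a rule along these lines:

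1. The baseline value is the latest measurement within a fixed look-back, for example 6 months, up to and including the section 3.6.3 baseline date that applies to the patient: switch or addition, first prescription, or 1 January 2000 for prevalent users.
2. For switchers and adders, the value must also have been taken during the regimen being left. For HbA1c it must have been taken long enough after that regimen began to reflect it; state the interval, with reference to the 1 to 4 months in section 3.4.4.
3. First-time and prevalent users need only the look-back. For prevalent users the start of the regimen may not be on record.
4. Any supplementary DNIP value is used only if its date meets the same conditions.
5. Report the distribution of the age of baseline values, and the number and characteristics of patients without an eligible value.
6. Repeat the analysis with 3- and 12-month look-backs.

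The cost is one rule applied to test and prescription dates already planned for extraction. The downside is that fewer patients contribute, and those who do are selected on having a recent test. Items 5 and 6 do not remove that selection, but they make it visible.

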6.1 Denmark

The Aarhus University Prescription Database records all reimbursed prescriptions dispensed in community pharmacies of the North and Central Denmark Regions – 2 of the 5 Danish regions, with combined population of 1.8 million, or 30% of the entire Denmark's population. Prescriptions for oral glucose-lowering medications are eligible for general reimbursement and are therefore recorded in this database; more than 98% of antidiabetic prescriptions are dispensed in the primary sector,² and are therefore expected to be recorded in this database. Recorded information includes the Anatomical Therapeutic Chemical classification of the drug, date of the dispensation, and unique product number.

Laboratory Information Systems for North and Central Denmark Regions (LABKA) track all hospital-performed laboratory tests, including those sent to hospital laboratories by general practice. The following data are recorded: the test name and IUPAC-code, the result, the measurement unit, the dates of ordering and carrying each test. The current coverage period for the Central Region ~ October 1999 to September of 2009, inclusive, for the North Region from 1997 to 2008, inclusive.

The Danish Central Personal Registry covers the entire Danish population and since 1968 has registered all births, deaths, and migration of Danish residents. This database contains dates of all recorded events and is updated daily.

The Danish Registry of Causes of Death contains information on causes of death, including associated diagnoses. Data have been collected since 1970.

The Danish National Registry of Patients covers the entire Danish population and has registered hospitalizations since 1977, including outpatient visits since 1995. Up to 20 discharge diagnoses are recorded for each hospital contact, using the International Classification of Diseases 10th revision (ICD-10) since 1994 and ICD-8 in the earlier period.

The Danish National Indicator Project (DNIP) was established in 1999 as a national quality monitoring and development project, aiming to measure and improve core healthcare services by means of indicators (indicator monitoring). During 2000–2008, disease-specific, evidence-based indicator sets for selected conditions –including diabetes – have been developed and implemented. The DNIP registration form for diabetic patients includes variables for date of diagnosis, date of diagnosis and type of diabetes, smoking habits, body mass index, blood pressure measurement, and HbA1c. This database is updated quarterly with a delay of one quarter. The latest update was in June 2010. Supplementary data on some rosiglitazone users may be available from the Danish National Indicator Project for Diabetes (DNIP)²², which was established in 1999 and collects annual measurements on HbA1c, smoking, body mass index, and blood pressure of diabetic patients in Denmark. For this project, we will apply for access and link the study population data with the DNIP files, although the extent of data overlap cannot be determined until the data are linked. Another shortcoming of these data is that only the most recent measurement in each calendar year is recorded, which does not necessarily represent the measurement most relevant to medication switch. At the same time, DNIP files may provide information on smoking and obesity for some of the diabetic patients.

Data linkage. All data sources listed above can be linked on patient level by the unique civil registration number, which is used to identify persons in all Danish registries. This number encodes person's sex and date of birth, enabling calculation of age at each time point or event.²³

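### Danish laboratory baselines can come from a hospital admission, because the latest pre-switch value is used whatever its setting; recovery may then be misread as a change after the switch

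*Protocol*

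**What the plan says.** Protocol section 3.4.4 names the Danish source: "Results of laboratory investigations will be ascertained from the Laboratory Information Systems of the North and the Central Denmark Regions (LABKA database) in Denmark". Section 6.1 says that these systems "track all hospital-performed laboratory tests, including those sent to hospital laboratories by general practice". General-practice samples are thus one part of a source that otherwise consists of hospital testing. On the content of each record, the same section says: "The following data are recorded: the test name and IUPAC-code, the result, the measurement unit, the dates of ordering and carrying each test". Neither care setting nor requester is listed.

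Section 3.6.4 fixes the contrast: "We will compare recorded plasma glucose concentration, HbA1c values, and other objective disease parameters before and after the baseline". It also fixes the baseline value: "The latest measurement before the baseline will be assumed to indicate the baseline value for the analysis". No limit is set on the setting of that measurement or on how far back it may lie. For follow-up it says: "We will conduct analyses examining 1, 3, and 6-month post-baseline changes in laboratory parameters". It further states: "We will compare measurements at various time points before and after the baseline".

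Among the glucose measures, section 3.4.4 lists "Treatment failure, defined as fasting plasma glucose level >180 mg per decilitre". Under section 3.6.3, baseline for a switcher is the recorded date of the switch, as shown by the new dispensation.

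**The concern.** A before-after change has no drug-free meaning unless the before value represents the patient's usual state. A value drawn during an acute admission may not, and taking the last value before the switch gives no protection when the admission is the most recent contact.

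The protocol's own set-up makes this possible. The Danish prescription database records dispensing in community pharmacies. If therapy were changed in hospital, the recorded switch could appear only after discharge, and the latest LABKA value before it could be an admission value. Sections 3.4.1 and 3.6.2 treat heart failure, ischaemic heart disease and acute coronary syndrome as contraindications, so an admission for one of these is a conceivable reason to leave rosiglitazone.

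At stake are the Danish changes in plasma glucose and in the parameters that section 3.4.5 uses as markers of kidney failure, liver failure and anaemia. The count of fasting values above 180 mg/dL is also exposed, since an illness-related value after baseline would enter it. Section 6.1 warns that the most recent yearly value in the National Indicator Project may not be the one most relevant to a switch. No such caution is attached to LABKA, and the discussion of bias in section 4 does not mention testing prompted by illness.

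**Working it through.** The protocol states no figure for this, so there is nothing to reproduce. What follows is an illustration with the true drug effect set to zero.

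**Inputs**
- From the protocol: about 2,400 Danish rosiglitazone users (section 3.3), which is an upper limit for those with laboratory data; an HbA1c averaging period of 1 to 4 months (section 3.4.4); a failure threshold of 180 mg/dL.
- Assumed: inpatient share of baseline values f_B and of follow-up values f_F, each 0 to 30%; inpatient glucose excess d of 2 to 4 mmol/L (36 to 72 mg/dL), the same before and after; duration of the excess 7 days; SD of change 40 to 60 mg/dL.

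**Mean change in glucose**

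Spurious fall after the switch = (f_B − f_F) × d.

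| f_B | f_F | d = 2 mmol/L | d = 4 mmol/L |
|---|---|---|---|
| 0.10 | 0 | fall 0.2 | fall 0.4 |
| 0.30 | 0 | fall 0.6 | fall 1.2 |
| 0.30 | 0.20 | fall 0.2 | fall 0.4 |
| 0.10 | 0.10 | 0 | 0 |
| 0.10 | 0.30 | rise 0.4 | rise 0.8 |

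The largest fall, 0.30 × 4 = 1.2 mmol/L, needs the highest assumed share, the highest assumed excess and no contamination at follow-up. Equal shares give zero. More admissions after the switch than before reverse the sign.

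**Scale**

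The 95% half-width of a mean change is 1.96 × SD / √n.
- n = 2,400: 1.96 × 40 / √2,400 = 1.6 and 1.96 × 60 / √2,400 = 2.4 mg/dL.
- n = 500 (assumed): 3.5 and 5.3 mg/dL.

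A net share of 10 percentage points with the smaller excess gives 0.10 × 36 = 3.6 mg/dL. That exceeds the half-width at 2,400 and is of the same order at 500.

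**HbA1c**

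With uniform weighting, a 7-day excess keeps 7/30 = 23% of its size over 1 month and 7/120 = 6% over 4 months. The 1.2 mmol/L upper bound becomes 1.2 × 7/30 = 0.28 or 1.2 × 7/120 = 0.07 mmol/L of average glucose.

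**Threshold count**

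With an excess of 36 to 72 mg/dL, a follow-up value crosses 180 mg/dL in a patient whose usual fasting level is above 180 − 36 = 144 or 180 − 72 = 108 mg/dL. If failure is counted only after baseline, contamination at baseline does not offset this.

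**The case against.** The strongest objection is that the protocol does not show the problem to occur. It does not say how many LABKA values are inpatient or that switches follow admissions, and the source also holds general-practice samples. That stands: the size and even the presence of bias are unknown.

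Further points stand in part:
- Appendix 1 heads the Danish glucose codes as fasting. This may keep out random inpatient glucose, but not fasting values taken during illness, and it does nothing for creatinine, ALAT or haemoglobin.
- Comparisons at several time points before baseline could reveal a transient value. No rule uses them to replace the baseline.
- Section 3.4.5 examines changes by pattern of drug use, and contamination common to all patterns would largely cancel between them. The before-after changes themselves would still carry it.
- The point concerns about 2,400 Danish users, against about 20,000 in the UK.
- Record exclusions and sensitivity analyses are commonly left to an analysis plan. The baseline rule, however, is already fixed in section 3.6.4, and that rule is what is questioned here.

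A reader might infer that acute values do become the Danish baselines, that spurious falls in glucose, creatinine and ALAT and rises in haemoglobin will follow, and that glucose will be off by 0.2 to 1.2 mmol/L. The documents do not support this. The range takes follow-up values as uncontaminated although the same source supplies them, it leaves out zero, and no direction is documented for any parameter. A difference in effect between Denmark and the UK is likewise only an inference from the GPRD's primary-care origin.

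**Conclusion.** The concern holds as a possible bias. The source includes inpatient tests, the baseline rule ignores setting, and nothing in the protocol screens such values from baseline or follow-up. Recovery may therefore be misread as a change after the switch in the Danish data, mainly for fasting glucose, creatinine, ALAT and haemoglobin. HbA1c, which the protocol calls a standard measure of long-term control, is largely protected by its averaging period.

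The net effect may be zero or of either sign. For glucose, 1.2 mmol/L is the upper bound on assumed inputs that have no source in the documents. A net inpatient share of about 10 percentage points would be enough to matter against sampling error if the SD of change is 40 to 60 mg/dL and most of the 2,400 users contribute. The planned linkage can measure the unknown share, so the point is worth settling before analysis.

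**What to change.** In section 3.6.4:
1. Flag every LABKA value dated from admission to discharge in the Danish National Registry of Patients. Sections 3.4.1 and 3.4.3 already use this registry, and section 6.1 makes it linkable by civil registration number. Use inpatient stays only, since the registry also holds outpatient visits. This assumes that admission and discharge dates are available; section 6.1 does not list them.
2. Report the flagged share before and after baseline, by parameter and by direction of switch.
3. Run the before-after analyses and the analysis of treatment failure above 180 mg/dL with flagged values excluded, taking the latest non-admission value as baseline. Show the all-values analysis beside it.

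The cost is one date-range match and a second set of tables. Some patients lose a baseline or follow-up value or fall back on an older baseline, and an inpatient value that prompted the switch would be set aside in the restricted analysis. Acute values just before admission or just after discharge remain, as does regression to the mean from a high general-practice result that led to a switch.
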